(CBT) states that it is not the situation itself but the thought associated with the situation (stimulus) which makes an individual fearful. Altering this thought and the emotions related to it is hence helpful in treating phobias. This was achieved by integrating an automated intelligent Cognitive Behavior Therapy software program with the VR device. 4) Finally, the researchers used Mindfulness Relaxation as a treatment for phobia. This was implemented by making the subject face the anxiety-provoking situation with the help of VR equipment and simultaneously working on reducing the anxiety emotions with the help of guided mindfulness meditation accompanied by meditation music, along with the developed automated intelligent therapy software interface. This methodology was intended to put the subject in a peaceful state of mind, detaching them from negative thoughts and fears, working on the principle that anxiety and relaxation cannot coexist.

[figure not shown]

Figure 6: Understanding CBT Software

Project Plan

[figure not shown]

Figure 7: Project plan

01/08/2020

OUTCOMES AND RESULTS

The quantitative and qualitative results were analyzed with the appropriate statistical and analytical tools. Various statistical modalities were used to establish efficacy, efficiency and the frequencies evaluated. Paired sample t- test were conducted in this study to assess the statistical significance of the interventions.

Independent sample t-test and ANOVA were tested in the data. Correlation analysis was also performed, The association between two categorical variables is enumerated by Chi-square test.

Scale	Mindfulness (n=118)		Control (n=125)		t-	F-	p-value
	Pre	Post	Pre	Post	value	value	
	Mean±SD		Mean±SD				
HAMA	32.86±5.76	19.62±4.24	33.70±6.08	28.00±6.49	8.350	2.327	0.000
SUDS	8.24±0.95	5.69±1.04	8.27±1.11	6.03±1.29	1.228	0.178	0.225
QOL	73.86±7.73	84.10±5.19	75.47±5.44	82.53±4.85	-2.229	6.242	0.030

Table 1: Mean comparison between Mindfulness Meditation group (n=118) and control group (n=125)

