Table 1 represents the mean comparison between Mindfulness group and the Control Group of respondents while before and after intervention. On The Hamilton Anxiety scale, most of the respondents in The Mindfulness Group had very severe condition while before intervention with mean score (M=32.86), but it reduced to mean score (M=19.62). While in the control group, most of the respondents had very severe condition while before intervention with mean score (M=33.70) and moderate to severe condition while after intervention with mean score (M=28.00). The obtained t-value and p-value for Hamilton scale are 8.350 and 0.000 respectively. Here, p-value is less than 0.01; it indicates that there is a statistically significant difference between mindfulness and control group of respondents based on Hamilton scale. Similarly when considered the Subjective Unites of Dysfunction Scale (SUDS), most of the respondents of The Mindfulness Group, felt 'Freaking out' while before intervention with mean score (M=8.24) and 'Moderately upset' while after

intervention with mean score (M=5.69). But in the control group, most of the respondents felt 'Freaking out' while before intervention with mean score (M=8.27) and 'bad' while after intervention with mean score (M=6.03). The obtained t-value and p-value for SUDS are 1.228 and 0.225 respectively. Here, p-value is greater than 0.05, and indicated that there is no significant difference between mindfulness and control group of respondents based on SUDS. Similarly, obtained t-value and p-value for Quality of life are -2.229 and 0.030. Here p-value is less than 0.05; and shows a statistically significant difference between Mindfulness and Control group in relation to WHO Quality of life (QOL - BREF) scale of respondents.

	CBT (n=106)		Control (n=125)				
Scale	Pre	Post	Pre	Post	t-	F-	p-
	Mean±SD		Mean±SD		value	value	value
HAMA	32.52±5.24	21.03±4.29	33.70±6.08	28.00±6.49	6.905	2.312	0.000
SUDS	8.24±0.98	5.34±1.14	8.27±1.11	6.03±1.29	2.366	0.344	0.021
QOL	73.62±5.23	83.28±5.06	75.47±5.44	82.53±4.85	-2.714	0.002	0.009

Table 1: Mean comparison between CBT group (n=106) and Control group (n=125)

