Table 2 presents the mean comparison between CBT group and control group of respondents before and after intervention. On the Hamilton Anxiety scale, most of the respondents of the CBT Group had very severe condition while before intervention with mean score (M=32.52), which reduced to mild to moderate severe after the intervention witj mean score (M=21.03). In control group, most of the respondents were in very severe condition while before intervention with mean score (M=33.70) and improved to moderate to severe condition after the intervention with mean (M=28.00). The obtained t-value and p-value for Hamilton scale are 6.905 and 0.000 respectively. Here, p-value is less than 0.01, it indicates a statistically significant difference between CBT and control group of respondents based on Hamilton Anxiety scale. Similarly, on the SUDS of respondents, most of the respondents felt 'Freaking out' while before intervention with mean (M=8.24) and

'Moderately upset' after the intervention with mean (M=5.34). But in the control group, most of the respondents felt 'Freaking out' before the intervention with mean (M=8.27) and felt 'bad' after intervention with mean (M=6.03). The obtained t-value and p-value for SUDS is 2.366 and 0.021 respectively. Here, p-value is less than 0.05, indicating a statistically significant difference between CBT and control group of respondents based on SUDS. Similarly obtained t-value and p-value for Quality of life are -2.714 and 0.009. Here p-value is less than 0.01; indicating a statistically significant difference between CBT and Control group in relation to The WHO Quality of life (QOL- BREF) scale of respondents.

	Novel IVRTS (n=115)		Control (n=125)		t-	F-	
Scale	Pre	Post	Pre	Post	_		p- value
	Mean±SD		Mean±SD		value	value	value
HAMA	28.60±8.45	11.10±4.03	33.70 ± 6.08	28.00±6.49	8.088	23.503	0.000
SUDS	8.10±1.56	3.73 ± 1.23	8.27±1.11	6.03 ± 1.29	7.503	2.315	0.000
QOL	72.87±6.21	87.07±3.79	75.47±5.44	82.53±4.85	-6.313	4.519	0.000

Table 3: Mean comparison between IVRTS (n=115) and Control group (n=125)

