Table 3 presents the mean comparison between The Novel Intelligent Virtual Reality Therapy System (IVRTS) and control group of respondents. On the Hamilton Anxiety scale of, most of the respondents of the Novel IVRTS Group had a score representing moderate to severe condition before the intervention with mean (M=28.60), and reduced to mild condition after the intervention with mean (M=11.10). In the control group, most of the respondents were in very severe condition before intervention with mean (M=33.70) and moved to moderate to severe condition after intervention with mean (M=28.00). The obtained t-value and p-value for Hamilton Anxiety scale is 8.088 and 0.000 respectively. Here, p-value is less than 0.01, it indicates that there is a statistically significant difference between The Novel IVRTS Group and The Control Group on Hamilton scale. Similarly, on the SUDS of respondents, most of the respondents of The IVRTS Group felt 'Freaking out' before the intervention (M=8.10) and 'No Significant Distress' after the intervention with mean

(M=3.73). In the control group, most of the respondents felt 'Freaking out' before the intervention with mean (M=8.27) and moved to feeling 'bad' after the intervention with mean with mean (M=6.03). The obtained t-value and p-value for SUDS are 7.503 and 0.000 respectively. Here, p-value is less than 0.01, it indicates that there is a statistically significant difference between The Novel IVRTS Group and The Control group based on SUDS. Similarly, the obtained t-value and p-value for The WHO Quality of life Scale were -6.313 and 0.009. Here p-value is less than 0.01, and indicates a statistically significant difference between The Novel IVRTS and Control group on The WHO Quality of life (QOL-BRF) scale of respondents.

Scale	Mindfulness		CBT		Novel IVRTS		
	Pre	Post	Pre Post		Pre	Post	
	Mean±SD		Mean±SD		Mean±SD		
HAMA	32.86±5.76	19.62±4.24	32.52±5.24	21.03±4.29	28.60±8.45	11.10 ± 4.03	
SUDS	8.24 ± 0.95	5.69 ± 1.04	8.24 ± 0.98	5.34 ± 1.14	8.10 ± 1.56	3.73 ± 1.23	
QOL	73.86±7.73	84.10±5.19	73.62±5.23	83.28±5.06	72.87±6.21	87.07±3.79	

Table 4: Efficacy of Interventions based on the HAMA, SUDS and WHO QOL scale

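### ANOVA is named but no identifiable ANOVA statistic is reported; the F column in Tables 1 to 3 is something else, and the claim that IVRTS beats CBT and Mindfulness has no test behind it

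*Combined protocol and SAP*

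**What the plan says.** The opening paragraph of Outcomes and Results lists the methods: paired t-tests, correlation, chi-square, and the sentence "Independent sample t-test and ANOVA were tested in the data". It gives no ANOVA factor, outcome or degrees of freedom.

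Tables 1 to 3 each compare one intervention with Control and print a t-value, an F-value and one p-value per scale. Table 1 is the "Mean comparison between Mindfulness Meditation group (n=118) and control group (n=125"); its HAM-A row ends "8.350 2.327 0.000". The CBT table (captioned Table 1, but called Table 2 in the text) is the "Mean comparison between CBT group (n=106) and Control group (n=125"). Table 3 sets IVRTS (n=115) against Control (n=125).

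The text under each table interprets only t and p, for example "obtained t-value and p-value for Quality of life are -2.714 and 0.009" for CBT and "The obtained t-value and p-value for SUDS are 7.503 and 0.000 respectively" for IVRTS. F is never mentioned.

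Table 4, the only table that sets the three interventions side by side, prints means and SDs and no test. The text on it then claims p below 0.01 for IVRTS against CBT, Mindfulness and Control, without naming a test. The abstract gives p < .001 for quality of life against Mindfulness and CBT, also without a test.

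**The concern.** ANOVA is the only F-based test that the methods name, so a reader will naturally take the F column for it. The column cannot be that analysis. If it is not, the stated ANOVA has no visible result.

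This matters because hypotheses (i) to (iii) set IVRTS against CBT and Mindfulness, as well as against Control in (ii) and (iii). Tables 1 to 3 compare each intervention only with Control. The direct comparisons rest on Table 4 and an unattributed p-value. HAM-A also differs at baseline between IVRTS and every other arm, and a comparison of raw post means ignores that difference.

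**Working it through.** **Inputs.** t, F, p and group sizes as printed in Tables 1 to 3; means and SDs as printed in Tables 1 to 4.

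**Step 1: is F the ANOVA of the printed t?** With two groups, F = t² on 1 and n₁+n₂−2 df, that is 241 (Mindfulness), 229 (CBT) and 238 (IVRTS).

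| Comparison with Control | t² | Printed F | p if F were ANOVA | Printed p |
|---|---|---|---|---|
| Mindfulness HAM-A | 8.350² = 69.72 | 2.327 | 0.13 | 0.000 |
| Mindfulness SUDS | 1.228² = 1.51 | 0.178 | 0.67 | 0.225 |
| Mindfulness QOL | 2.229² = 4.97 | 6.242 | 0.013 | 0.030 |
| CBT HAM-A | 6.905² = 47.68 | 2.312 | 0.13 | 0.000 |
| CBT SUDS | 2.366² = 5.60 | 0.344 | 0.56 | 0.021 |
| CBT QOL | 2.714² = 7.37 | 0.002 | 0.96 | 0.009 |
| IVRTS HAM-A | 8.088² = 65.42 | 23.503 | 0.000002 | 0.000 |
| IVRTS SUDS | 7.503² = 56.30 | 2.315 | 0.13 | 0.000 |
| IVRTS QOL | 6.313² = 39.85 | 4.519 | 0.035 | 0.000 |

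F differs from t² in 9 of 9 rows. In five (Mindfulness HAM-A, all three CBT rows, IVRTS SUDS) F would be non-significant at 0.05 beside a printed p below 0.05. The same five rows result with 57 error df.

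**Step 2: is F some other group comparison?** From the printed means, SDs and n, a post-score ANOVA gives 140.2, 5.08 and 5.94 (Mindfulness); 89.2, 18.2 and 1.32 (CBT); 575.5, 199.1 and 64.5 (IVRTS). Baseline scores, change scores (pre-post correlation assumed 0, 0.5, 0.9) and ANCOVA (assumed 0 to 0.9) do not reproduce the column either. An omnibus test would give one F per scale, whereas the printed F differs between tables.

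**Step 3: is F a variance test?** A plain variance ratio does not fit: IVRTS HAM-A post is (6.49/4.03)² = 2.59 against 23.503. A Levene-type statistic needs individual data, so it can be neither confirmed nor excluded. On that reading, 6.242, 23.503 and 4.519 would reject equal variances (p = 0.013, 0.000002 and 0.035). The tables do not say whether the printed t is pooled or unequal-variance.

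**Step 4: which n and which score lie behind t?** At 241 df, t = 1.228 and 2.229 give p = 0.221 and 0.027, against printed 0.225 and 0.030. At 229 df, t = 2.366 and 2.714 give 0.019 and 0.007, against 0.021 and 0.009. All four printed values fit about 57 df. Nor are the HAM-A t-values post-score t-values at the printed n: those would be 11.84, 9.44 and 23.99 in absolute value, against 8.350, 6.905 and 8.088.

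**Step 5: what could baseline adjustment do on HAM-A?** The documents give no pre-post correlation r, so r is an assumption. Pooled within-arm SDs over the four arms are 6.51 (pre) and 4.91 (post), ratio 0.755. The slope is b = 0.755r, and the adjusted difference is the post difference − b × the pre difference.

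| IVRTS minus | Post difference | Pre difference | Adjusted, r = 0.5 | Adjusted, r = 0.9 |
|---|---|---|---|---|
| CBT | 11.10 − 21.03 = −9.93 | 28.60 − 32.52 = −3.92 | −8.45 | −7.27 |
| Mindfulness | 11.10 − 19.62 = −8.52 | 28.60 − 32.86 = −4.26 | −6.91 | −5.63 |
| Control | 11.10 − 28.00 = −16.90 | 28.60 − 33.70 = −5.10 | −14.97 | −13.43 |

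This assumes one slope for all arms and the printed n as weights.

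**The case against.** The column is headed only as an F-value, and nothing ties it to ANOVA. An F printed beside an independent-samples t, with a single p that follows the t, is a familiar layout for t-test output with a variance-equality check. The ANOVA reading fails in every row, so it is the less plausible of the two. On the likelier reading the column is under-labelled and no number in it is shown to be wrong. This stands. A reader might infer from the table above that five significant results are contradicted; the documents do not support that, because they never present these F-values as ANOVA results or use them for any conclusion.

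The three possible rejections of equal variance also have no demonstrated effect. On post scores the unequal-variance t² is within about 7% of the pooled F, and the authors may already have used the unequal-variance form. This stands too.

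Planned pairwise comparisons are legitimate without an omnibus F, so the absence of a joint F-test is not itself a defect. Nor can one say that no ANOVA was performed: the p-values in the abstract and in the text on Table 4 might come from one.

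What the objection does not reach is the missing comparison of IVRTS with CBT and Mindfulness. Relabelling the F column would leave that claim as unsupported as before.

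**Conclusion.** The point holds in a limited form. ANOVA is named, no identifiable ANOVA statistic is reported, and the F column is not a two-group ANOVA matching the printed t (9 of 9 rows). That the column is a variance test is probable but is an inference. The substantive gap is that the p below 0.01 for IVRTS against CBT and Mindfulness cannot be traced to any test, statistic, df or interval, on data where IVRTS began 3.92 to 5.10 HAM-A points below the other arms.

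A reader might go further and infer that the treatment conclusion is wrong. The documents do not show that. Over assumed correlations from 0 to 0.9, the adjusted HAM-A differences shrink but still favour IVRTS. Their precision cannot be given, because the numbers analysed are in doubt: four printed p-values fit about 57 df rather than 229 to 241.

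**What to change.** For each scale, fit one four-arm ANCOVA of the post score on arm and pre score, with standard errors robust to unequal variances. Report the contrasts of IVRTS with CBT, Mindfulness and Control, each with its estimate, 95% CI, df, p and the n analysed. Base the claim under Table 4 and the matching abstract statement on these contrasts.

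In Tables 1 to 3, name the test behind each F or remove the column. State which score the t compares, whether it is pooled or unequal-variance, and its df.

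The cost is a re-run on data already collected and re-issued tables. The authors should expect that the adjusted HAM-A differences may be less favourable to IVRTS than the raw post-score differences.

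### The printed t- and p-values imply about 60 patients per comparison, not the 243 and 231 in the table captions, so the group sizes or the test results are wrong as written.

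*Combined protocol and SAP*

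**What the plan says.** The Sample section describes 500 patients randomised, 125 to each of four arms. The results tables give smaller numbers for three arms: 118 (Mindfulness), 106 (CBT), 115 (IVRTS) and 125 (control), 464 in all.

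Under Outcomes and Results, the between-group method is given as "Independent sample t-test and ANOVA were tested in the data". The captions are:
- "Table 1: Mean comparison between Mindfulness Meditation group (n=118) and control group (n=125"
- "Table 1: Mean comparison between CBT group (n=106) and Control group (n=125" (numbered 1 again; the text calls it Table 2, as I do here)
- "Table 3: Mean comparison between IVRTS (n=115) and Control group (n=125"

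The text then repeats the table entries, for example "The obtained t-value and p-value for SUDS are 1.228 and 0.225 respectively" for Mindfulness, "The obtained t-value and p-value for SUDS is 2.366 and 0.021 respectively" for CBT and, for IVRTS, "The obtained t-value and p-value for Hamilton Anxiety scale is 8.088 and 0.000 respectively". For IVRTS quality of life the text gives "The WHO Quality of life Scale were -6.313 and 0.009", while Table 3 prints p = 0.000 for the same t. No df, confidence interval or smaller analysis set appears in the readable text, and it is not said whether the post-treatment score or the change score was tested.

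**The concern.** For a given test, t and df determine p, so a printed t and p can be turned back into df and hence the number of patients analysed. Done here, the answer is about a quarter of the captioned numbers.

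The conclusions on Mindfulness and CBT against control are read straight from these pairs, and the t-values in the IVRTS table show a matching problem. If the captions are right, the test results are wrong. If the tests are right, the analysed sample is far smaller than the report says, and every comparison is about half as precise as its caption implies.

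**Working it through.** **1. p at the captioned sizes.** For a pooled two-sample test, df = n1 + n2 − 2: 118 + 125 − 2 = 241 and 106 + 125 − 2 = 229. Two-sided p = 2·P(T_df > |t|). An unequal-variance test cannot have fewer df than the smaller arm minus one (117 and 105), so that is the floor.

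| Row | t | p printed | p at 241 / 229 | p at floor 117 / 105 | df that reproduce printed p |
|---|---|---|---|---|---|
| Mindfulness SUDS | 1.228 | 0.225 | 0.221 | 0.222 | 47–59 |
| Mindfulness QOL | −2.229 | 0.030 | 0.027 | 0.028 | 48–61 |
| CBT SUDS | 2.366 | 0.021 | 0.019 | 0.020 | 56–77 |
| CBT QOL | −2.714 | 0.009 | 0.007 | 0.008 | 44–65 |

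The last column allows for rounding of both t and p. No row matches at the captioned sizes or at the floor. One-sided p-values at df 241 and 229 are 0.110, 0.013, 0.009 and 0.004, so sidedness does not explain it.

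**2. Which df fit.** Table 1 alone allows df 48–59 (50–61 patients) and Table 2 alone 56–65 (58–67 patients). All four rows share only 56–59 (58–61 patients). At df 57 the p-values are 0.2245, 0.0298, 0.0214 and 0.0088.

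**3. t from the printed post-treatment means and SDs.** With the pooled variance sp² = [(n1−1)s1² + (n2−1)s2²]/(n1+n2−2), t = (control mean − therapy mean)/√[sp²(1/n1 + 1/n2)]. For Mindfulness SUDS: sp² = (117·1.04² + 124·1.29²)/241 = 1.381; SE = √[1.381(1/118 + 1/125)] = 0.151; t = (6.03 − 5.69)/0.151 = 2.25, p = 0.025, against the printed 1.228 and 0.225.

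**4. t as a change-score test.** The variance of change in an arm is s_pre² + s_post² − 2r·s_pre·s_post. The pre-post correlation r is not reported, so I assume one common r in both arms and solve for the r that returns the printed t.

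| Row | t printed | Post-score t, stated n | Post-score t, 29–30 per arm | r needed, stated n | r needed, 29–30 per arm |
|---|---|---|---|---|---|
| Mindfulness HAM-A | 8.350 | 11.84 | 5.85 | 0.25 | 0.83 |
| Mindfulness SUDS | 1.228 | 2.25 | 1.11 | −0.58 | 0.62 |
| Mindfulness QOL | −2.229 | −2.44 | −1.20 | −0.82 | 0.60 |
| CBT HAM-A | 6.905 | 9.44 | 4.85 | 0.37 | 0.84 |
| CBT SUDS | 2.366 | 4.27 | 2.17 | −0.72 | 0.56 |
| CBT QOL | −2.714 | −1.15 | −0.58 | 0.01 | 0.75 |
| IVRTS HAM-A | 8.088 | 23.99 | 12.12 | −0.60 | 0.70 |
| IVRTS SUDS | 7.503 | 14.11 | 7.07 | −0.43 | 0.66 |
| IVRTS QOL | −6.313 | −8.03 | −4.04 | −0.47 | 0.68 |

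Post scores reproduce the printed t-values at neither size. A free r can be made to fit each row, so the test is plausibility. At the stated n, six of nine rows need a clearly negative correlation between a patient's own scores before and after. At 29 (Mindfulness, CBT) and 30 (IVRTS, control) per arm, all nine need 0.56 to 0.84, and 29 + 30 − 2 = 57 lies inside the df range of step 2.

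**5. What depends on the answer.**

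*If the stated n is right:*
- Mindfulness SUDS, reported as non-significant, becomes significant on post scores (p = 0.025). On change scores it does so from r of about 0.40 (p = 0.048; p = 0.014 at r = 0.62); at r = 0 it does not (p = 0.124).
- CBT QOL loses significance only if post scores were tested (t = −1.15, p = 0.25). On change scores it stays significant (p = 0.007 at r = 0).

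*If 29 to 30 per arm is right:*
- The analysed total is 29 + 29 + 30 + 30 = 118, and the standard errors against control are 1.97 to 2.03 times those at the stated n.
- The IVRTS minus control HAM-A change, (11.10 − 28.60) − (28.00 − 33.70) = −11.8, has a 95% CI of −14.7 to −8.9 rather than −13.2 to −10.4 (assumed r = 0.70).
- IVRTS against Mindfulness on QOL gives p = 0.015 on post scores and 0.009 to 0.004 on change scores for r of 0.6 to 0.7. The abstract's p < .001 would need r of about 0.80.

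At 30 per arm, IVRTS against control has p of at most 0.0004 on every scale, on post scores or on change scores with r of zero or more.

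**The case against.** The best case for the authors has four parts.

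First, the df conflict moves p by at most about 0.004 and changes no significance call. The informative pairs concern Mindfulness and CBT against control, whereas the stated hypotheses compare IVRTS with the other groups. That is true, and it limits what the mismatch alone does to the conclusions. It does not restore the sample size.

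Second, the CONSORT diagram (Figure 5) is not readable here and may show a smaller analysed set. That stands as a limit on any claim of non-disclosure, which I confine to the text. The diagram could not reconcile captions that print 118, 106 and 125 with these p-values.

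Third, the two tables need not share one df, and 29 to 30 per arm is softer than the df conflict. Table 3 prints only p = 0.000, which carries no df information, so the IVRTS arm rests on an assumed change-score test with a common r. Whole-number scores give some support: 29 for Mindfulness and CBT, and 30 for IVRTS and control, yield all six printed means per arm. Larger sizes fit too (58 for Mindfulness and CBT, 60 for IVRTS and control, and any size above 100). This part is inference. The per-table df ranges are still far from 241 and 229.

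Fourth, the reversals in step 5 are conditional on the score tested and on r. They are, and are presented so.

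The F column gives no way out. It is not t² (8.350² is about 69.7, against F = 2.327), and the text does not say what it tests.

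**Conclusion.** The concern holds. For Tables 1 and 2 the captioned group sizes and the printed t/p pairs cannot both be right. This needs no assumption about which score was tested, only that p comes from a t-distribution; the equal-variance, unequal-variance and one-sided versions all fail.

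That the true analysed size was about 29 to 30 per arm is well supported but not proven. It rests on a change-score test, one common pre-post correlation and, for the supporting check on means, whole-number scores. The documents cannot show whether the sizes or the test results are the error.

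The analysed total may therefore be 464 or about 118. The superiority of IVRTS over control survives either way. The Mindfulness SUDS result, the CBT QOL result and the abstract's p < .001 against Mindfulness on QOL remain open until the size and the score are known.

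The IVRTS QOL p-value in the text (0.009) is a separate slip: t = −6.313 gives p < 0.001 at either size, in line with Table 3.

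**What to change.** Re-run all nine comparisons with control from patient-level data. State whether the post score or the change score is tested, and say what the F column is. Print n per arm, df, mean difference and 95% CI in every row.

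- If the analysed set was smaller, replace 500, 125 and 118/106/115/125 wherever they describe the analysed sample, account for the remaining patients, and restate precision and conclusions at that size, including the IVRTS comparisons with Mindfulness and CBT in the abstract and under Table 4.
- If 464 were analysed, replace the printed t- and p-values and any significance statement that changes.

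In either case, correct the 0.009 in the text under Table 3 and renumber the second table. The cost is re-running existing analyses and correcting tables and text; no new data are needed.

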In this health-related research, the researchers first applied to health research ethics committees for permissions and once the permissions are taken, then the researchers identified the sample or user groups, through seminars at the Gjøvik hospital, using social media, etc. The researchers made sure that the user consent is received, the participation in our studies are voluntary and their participation can be ended any time by the user without any penalties for the user. Also, the Clinical Trials took place at The Psychiatry OPD of the Guru Tegh Bahadur Hospital of The University of Delhi.

Figure 4: The software detects the pupil, after detection it determines the focus point of gaze to control the virtual interaction

Hypothesis:

- (i) The new novel developed technology Intelligent Virtual Reality Therapy System (IVRTS) is more effective in reducing symptoms of Phobia and Anxiety as compared to Mindfulness Meditation and Cognitive Behavior Therapy Groups.
- (ii) The novel IVRTS Group scores significantly lower on both Hamilton Anxiety Inventory (HAM-A) and Subjective Units of Dysfunction Scale (SUDS) compared to all three, The Control Group, The Mindfulness Group Cognitive Behavior Therapy (CBT) Group.
- (iii) The Novel IVRTS Group scores significantly higher on WHO Quality of Life Scale (WHO QOL BREF) compared to all three, The Control Group, The Mindfulness Meditation Group and The CBT Group.
- (iv) The new technology proves to be effective and a steppingstone towards a newer era in the treatment of Mental Health issues using Mental healthcare engineering.

Sample

The Clinical Trials were carried out on 500 adults with Acrophobia which is fear of heights co-morbid with Generalized Anxiety. The sample for the study was recruited from the patients/subjects attending the adult psychiatric OPD of the department of Psychiatry GTB Hospital of The University of Delhi and fulfilling the

ICD-10 diagnostic criteria for assessment of Acrophobia and generalized anxiety. The study was conducted on an initial 500 subjects attending the psychiatric OPD of the department of Psychiatry GTB Hospital of the University of Delhi. The subjects were equally and randomly assigned to three groups namely; Novel Intelligent Virtual Reality System (IVRTS) Group (n=125), Mindfulness Meditation Group (n=125), Cognitive Behavior Therapy (CBT) Group (n=125) and The Control Group (n=125).

[figure not shown]

Figure 5: Consort Diagram

Inclusion Criteria

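### By their printed n the arm-versus-control tables omit 36 of the 500 randomised patients, all from active arms, and the printed t and p-values do not fit those n either

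*Combined protocol and SAP*

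**What the plan says.** The Sample section describes equal random allocation of 500 patients, 125 to IVRTS and then "Mindfulness Meditation Group (n=125), Cognitive Behavior Therapy (CBT) Group (n=125) and The Control Group (n=125"). Procedure and Approaches says that 500 patients underwent the intervention, for 3500 sessions in total (500 × 7).

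OUTCOMES AND RESULTS uses other numbers. The first table is captioned "Table 1: Mean comparison between Mindfulness Meditation group (n=118) and control group (n=125"). The second, numbered Table 1 again although the text calls it Table 2, is captioned "Table 1: Mean comparison between CBT group (n=106) and Control group (n=125"). Table 3 gives IVRTS 115 and control 125. Table 4, which carries the comparison of the three active arms, shows no n, t or p; the text on it says only that p is below 0.01.

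The method is described as "Independent sample t-test and ANOVA were tested in the data". Whether post scores or changes were tested is not said. The visible text names no analysis set and no handling of missing outcomes. A flow diagram exists ("Figure 5: Consort Diagram"), but the image is not available here.

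Four results come with a p-value precise enough to check:
- Mindfulness–control SUDS: "The obtained t-value and p-value for SUDS are 1.228 and 0.225 respectively".
- Mindfulness–control quality of life: "obtained t-value and p-value for Quality of life are -2.229 and 0.030".
- CBT–control SUDS: "The obtained t-value and p-value for SUDS is 2.366 and 0.021 respectively".
- CBT–control quality of life: t = −2.714, p = 0.009.

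**The concern.** There are two linked problems. First, taken at face value, the labels set reduced treated arms against a complete control arm. A contrast of that kind loses the protection of randomisation: it would favour treatment if the absent patients did worse, and the documents do not show whether they did. Second, the reported t and p-values should follow from the labelled n, and they do not. At stake are the size and precision of the effects against control, and the sample size on which all the efficacy conclusions rest.

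**Working it through.** **Counts.** Allocated: 4 × 125 = 500. Labelled: 118 + 106 + 115 + 125 = 464. Absent by label: Mindfulness 7 (5.6%), CBT 19 (15.2%), IVRTS 10 (8.0%), control 0; in total 36 (7.2%).

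**Degrees of freedom.** This check needs only each printed t and its p, not the means, the SDs or the choice of score. p = 2 × P(T > |t|), with df = n₁ + n₂ − 2. The labels give 118 + 125 − 2 = 241 and 106 + 125 − 2 = 229.

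| Contrast | t | p printed | p at labelled df | df that fit, allowing for rounding of t and p |
|---|---|---|---|---|
| Mindfulness SUDS | 1.228 | 0.225 | 0.2206 | 47–59 |
| Mindfulness QOL | −2.229 | 0.030 | 0.0267 | 48–61 |
| CBT SUDS | 2.366 | 0.021 | 0.0188 | 56–77 |
| CBT QOL | −2.714 | 0.009 | 0.0072 | 44–65 |

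None of the four is reproduced, and all miss in the same direction. The smallest df that a Welch test could give at the labelled n (117 or 105) also fails: 0.2219, 0.0277, 0.0198, 0.0078. Within each contrast the ranges overlap at 48–59 (Mindfulness) and 56–65 (CBT). Adding 2 gives about 50–61 and 58–67 patients, against 243 and 231 by label. The IVRTS p-values are printed in Table 3 as 0.000 and carry no information on df.

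**Post-score t at the labelled n.** t = (control mean − arm mean) / [s_p √(1/n₁ + 1/n₀)], with s_p the pooled SD. For IVRTS HAM-A, s_p = 5.452 and t = 16.90 / (5.452 × 0.1292) = 23.99; the printed value is 8.088.

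| Recomputed / printed t | HAM-A | SUDS | QOL |
|---|---|---|---|
| Mindfulness | 11.84 / 8.350 | 2.25 / 1.228 | −2.44 / −2.229 |
| CBT | 9.44 / 6.905 | 4.27 / 2.366 | −1.15 / −2.714 |
| IVRTS | 23.99 / 8.088 | 14.11 / 7.503 | −8.03 / −6.313 |

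None of the nine reproduces. The errors go both ways: eight recomputed values are larger than printed, and CBT QOL is smaller.

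**Change-score t (assumption: changes were tested, with one common pre–post correlation r in both arms).** The change variance is s_pre² + s_post² − 2·r·s_pre·s_post. Set the pooled value equal to (d/t)² / (1/n₁ + 1/n₀) and solve for r. For IVRTS HAM-A, d = 17.50 − 5.70 = 11.80 and the required variance is (11.80/8.088)² / 0.0167 = 127.5. The pooled s_pre² + s_post² is 83.2 and the pooled 2·s_pre·s_post is 73.7, so r = (83.2 − 127.5) / 73.7 = −0.60.

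| r needed: labelled n / 29–30 per arm | HAM-A | SUDS | QOL |
|---|---|---|---|
| Mindfulness | 0.25 / 0.83 | −0.58 / 0.62 | −0.82 / 0.60 |
| CBT | 0.37 / 0.84 | −0.72 / 0.56 | 0.01 / 0.75 |
| IVRTS | −0.60 / 0.70 | −0.43 / 0.66 | −0.47 / 0.68 |

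At the labelled n, six of nine need a negative correlation, −0.43 to −0.82, which is implausible for repeated scores on one scale. With 29 patients (Mindfulness, CBT) and 30 (IVRTS, control), all nine need 0.56 to 0.84.

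**Printed means.** If individual scores are whole numbers (assumption), 29 and 30 also fit all six means of the respective arms. So do other n: 40 and 60 for control and IVRTS, 42 and 58 for Mindfulness, 58 for CBT, and many from 64 upwards, including the labelled n.

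**Size, if the labels are right.** Unadjusted difference in mean change from control, with absent patients (a) unchanged: arm change × n/125; or (b) improving as control did: add control change × (125 − n)/125.
- IVRTS–control HAM-A, printed: 17.50 − 5.70 = 11.80. (a) 17.50 × 115/125 − 5.70 = 10.40. (b) 10.40 + 5.70 × 10/125 = 10.86.
- CBT–control SUDS, printed: 2.90 − 2.24 = 0.66. (a) 2.90 × 106/125 − 2.24 = 0.22. (b) 0.22 + 2.24 × 19/125 = 0.56.

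**The case against.** The strongest reply has four parts.

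- The flow diagram may already give the losses and reasons, and the Sample section speaks of an initial 500. This stands as far as reporting goes. It does not change the labelled contrasts, which still leave those patients out, and the statement that 500 underwent the intervention still has to be reconciled with them.
- The two halves pull against each other: the loss percentages and scenarios assume the labels are right, and the df check says they may not be. This is correct. The scenario figures therefore apply only if the labels are confirmed.
- A misprint or an unstated model could explain the mismatch. This cannot be excluded, though four p-values all missing in the same direction make an isolated misprint a weak explanation. For IVRTS the doubt rests only on t-values that do not reproduce.
- The scenarios are unadjusted, while IVRTS began 5.10 HAM-A points below control (28.60 against 33.70), so they do not estimate the baseline-adjusted effect. This also stands.

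A reader might infer that only 29 or 30 per arm were tested, 118 in all, with 382 patients outside the tests. The documents do not support that as a fact. Other n fit the means, the two contrasts give different df ranges, and the IVRTS p-values say nothing about df.

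**Conclusion.** The point holds. By label, 36 of 500 randomised patients are outside the contrasts with control, all from active arms. Independently, the labelled n conflict with the printed t and p-values for Mindfulness and CBT, which fit roughly 50–67 patients per contrast. The count rests on the printed n alone. The df result assumes an ordinary two-sample t-test with correctly printed t and p. The correlation argument assumes change scores and a common correlation.

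Two stronger readings are tempting and not supported. One is that the exclusions inflate the treatment effects: the outcomes of the absent patients are not given, so the direction is unknown. The other is that reported findings collapse. In the scenarios shown the effects shrink but keep their direction, and since the post-score tests do not reproduce the reported t-values, they cannot show that any result loses significance. Equally, if the labels are wrong, the scenarios give no reassurance.

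**What to change.** 1. Confirm for each contrast the n tested and whether post or change scores were used, and correct the labels or the t and p-values. If far fewer than 464 were tested, state how those patients were chosen from the 500 and restate the sample size behind the conclusions. Report losses and reasons by arm if the flow diagram does not.
2. Re-run every contrast, including IVRTS against CBT and against Mindfulness behind Table 4, on all randomised patients with outcome data, in their randomised groups and adjusted for baseline. Print n, estimate and confidence interval. With one baseline and one post score, multiple imputation or a likelihood model would add almost nothing to this, so it need not be the core of the change.
3. Add sensitivity analyses over all 500, with missing patients (a) unchanged and (b) improving as control did.

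The cost is extra analysis work, and some effects against control may shrink. Baseline scores must be held for the missing patients. If the tested n was much smaller than the labels, the re-run also needs outcome data for the remaining patients, which the documents do not show to exist.
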